6.4.4 Subpopulation s

Treatment group differences for the primary efficacy endpoint will be summarized descriptively for the following subpopulations based on the following baseline characteristics:

- Gender (female, male)
- Race (Asian, African-American, Caucasian, other)
- Ethnicity (Hispanic, non-Hispanic)
- Ventricular morphology (single left, single right or mixed)
- Age at Fontan surgery (< 3 years, \geq 3 years)
- Baseline serum BNP level (< median, \geq median)
- Percent of predicted maximal VO_2 at baseline (< 75%, \geq 75%)

A 95% confidence interval of the difference in treatment group means will be provided within each subpopulation.

6.4.5 Adjustments for Multiple Comparisons

Formal hypothesis testing will be performed only for the primary efficacy endpoint. Thus, no adjustment for multiple comparisons will be necessary.

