11.4 Efficacy Results and Tabulations of Individual Subject Data

11.4.1 Analysis of Efficacy

The primary aim of this study was to evaluate the effect of 26 weeks of treatment with udenafil on exercise capacity in adolescents with Fontan physiology, with a primary outcome of change in maximal VO_2 from baseline to Week 26. The udenafil group had a mean increase from baseline to Week 26 in maximal VO_2 compared to a mean decrease in the placebo group, and the primary analysis identified a statistical trend for the treatment difference ($p=0.071$). Importantly, all efficacy endpoints measured at VAT indicated greater exercise capacity in the udenafil group than the placebo group at Week 26 ($p\leq 0.05$).

After an initial summary of the protocol-specified primary endpoint (maximal VO_2), this summary of efficacy will focus on measures of exercise capacity at VAT. In addition, maximal VO_2 and VO_2 at VAT were summarized with units of mL/min in addition to the protocol-specified units of mL/kg/min. As each participant's VO_2 at Week 26 is compared to their baseline, the natural fluctuations in weight over 6 months would add variability and could be a source of bias for individual subjects and for the study population as a whole.

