impact of alterations in PVR on exercise capacity for those with other forms of heart disease. Although udenafil may have some effect on maximal VO₂, this effect is blunted by the physiologic ceiling of CVP. The expanded understanding of Fontan physiology in recent years has taught that the assumptions informing the selection of maximal VO₂ as the primary endpoint were inaccurate, and that VO₂ at VAT is a more useful endpoint for this unique cohort of patients.

Overall Efficacy Conclusions

In summary, treatment with udenafil for 26 weeks resulted in improvements in exercise capacity, as well as an improvement in the performance of the single ventricle. Although the primary endpoint did not reach statistical significance, new knowledge of the limits of the Fontan circulation explains why this endpoint is an imperfect choice for this circulation. Even with the limitations associated with maximal VO₂, this endpoint showed a clear trend toward improvement that, coupled with the improvement at the anaerobic threshold, speaks to the efficacy of udenafil to improve exercise capacity in this population. Based on the superior exercise capacity and ventricular performance for udenafil as compared to placebo at Week 26, this study achieved its primary clinical objective for a population with no pharmacotherapeutic options.

12 Safety Evaluation

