6.0 Statistics

All statistical tests will be at the 0.05 alpha level, 2-tailed, unless stated otherwise. Probabilities will be rounded to 4 decimal places before assigning statistical significance.

Descriptive statistics for categorical endpoints will include the number and percent of subjects in each treatment group and category. Quantitative endpoints will be summarized for each treatment group with the mean, median, standard deviation, minimum value, and maximum value.

Individual subject data will be presented in data listings, which will include normal reference ranges when appropriate.

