6.4.2 Secondary Efficacy Endpoints

Secondary efficacy endpoints include change from baseline to Visit 4 (Week 26) in:

- Exercise capacity
 - Minute oxygen consumption at the ventilator anaerobic threshold (VAT)
 - Ventilatory equivalents of carbon dioxide (VE/VCO₂) at VAT
 - Respiratory rate and minute ventilation at peak exercise
 - Maximal work rate
 - Work rate at the VAT
- Ventricular performance
 - Myocardial performance index (MPI) determined by velocities obtained from blood pool Doppler assessment of the inflow and outflow tract of the dominant ventricle. It is the primary performance endpoint of the echocardiogram.
 - Ventricular cavity size, eccentricity, and mass (based on echocardiogram)
 - Systolic function estimate using mean dP/dt during isovolumetric contraction (dP/dt_{ic}) and peak systolic annular velocity (S') on tissue Doppler
 - Qualitative and quantitative estimate of atrioventricular valve insufficiency
- Endothelial function: log-transformed reactive hyperemia index (lnRHI), as measured by pulse amplitude tonometry (PAT) testing using the EndoPAT® device
- Natural logarithm transformation of BNP
- Functional health status as measured by the full scale PedsQL
 - Physical functioning score

CONFIDENTIAL

- Psychosocial functioning score
- Cardiac-specific quality-of-life score
- Pediatric Cardiac Quality of Life Inventory (PCQLI) score

Each secondary efficacy endpoint will be summarized descriptively by treatment group.

Treatment group differences for endpoints associated with the PedsQL and PCQLI will be assessed with Friedman's test using ventricular morphology (single left versus single right or mixed) as the stratification factor. The treatment group difference for the qualitative estimate of atrioventricular valve insufficiency will be assessed with a Cochran-Mantel-Haenszel test using ventricular morphology (single left versus single right or mixed) as the stratification factor.

The remaining secondary efficacy endpoints will be analyzed with the ANCOVA model with fixed factors for ventricular morphology (single left versus single right or mixed) and treatment group with a covariate for the baseline value.

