6.4.3 Missing Data

The following imputation method will be used for the primary analysis of the primary outcome:

- Subjects who have died or have dropped out of the study with unknown vital status will be assigned a maximal VO₂ of zero at Visit 4.
- Subjects who are known to be alive, but who discontinued from the study (and are missing maximal VO₂ at Visit 4) will be assigned the latest value available (e.g., value from end of study visit if available, and from baseline visit otherwise).
- Subjects who complete Visit 4, but are physically unable to reach maximum effort in cardiopulmonary exercise testing after two attempts, will be assigned their baseline value (i.e., zero change).

Two additional analyses to assess the impact of missing data will be conducted as follows:

- Subjects with missing maximal VO₂ at Visit 4 will be assigned a maximal VO₂ of zero
- Subjects with missing maximal VO₂ at Visit 4 will be excluded from analysis (i.e., observed cases analysis).

Missing item scores for rating scales will be imputed according to published methodology for the scale. Otherwise, missing data will not be estimated for secondary efficacy endpoints.

CONFIDENTIAL

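### SAP 6.4.5 confines formal testing to the primary endpoint, but secondary tests are planned at 0.05 without being called nominal, and the report rests its efficacy conclusion on them after the primary missed

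*SAP*

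**What the plan says.** The document supplied as the protocol is written as a clinical study report and is called the report here.

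- **SAP 6.4.5:** "Formal hypothesis testing will be performed only for the primary efficacy endpoint. Thus, no adjustment for multiple comparisons will be necessary". Report 9.7.1 and 11.4.2.5 repeat the restriction to the primary, and 11.4.2.5 confirms that the secondaries were not adjusted.
- **SAP 6.4.2:** quality-of-life endpoints get a test ("Treatment group differences for endpoints associated with the PedsQL and PCQLI will be assessed with Friedman's test"), qualitative valve insufficiency gets a Cochran-Mantel-Haenszel test, and for the rest "The remaining secondary efficacy endpoints will be analyzed with the ANCOVA model with fixed factors for ventricular morphology", with treatment group and the baseline value in the model.
- **SAP 6.0:** "All statistical tests will be at the 0.05 alpha level, 2-tailed, unless stated otherwise".
- **SAP 6.4.3**, on secondaries, after the rule for rating-scale items: "Otherwise, missing data will not be estimated for secondary efficacy endpoints". Observed cases is therefore the planned analysis for the exercise secondaries.
- **Report 11.4.1:** "all efficacy endpoints measured at VAT indicated greater exercise capacity in the udenafil group than the placebo group at Week 26", with p≤0.05 as the criterion.
- **Report 11.4.7:** after conceding that the primary was not significant, it says that the trend in maximal VO2, "coupled with the improvement at the anaerobic threshold, speaks to the efficacy of udenafil to improve exercise capacity in this population". It then states that the study met its primary clinical objective. Section 13 concludes likewise and says improved exercise capacity was demonstrated.

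**The concern.** A plan with one formal test and nominal secondary analyses is coherent, provided that nothing is claimed from the secondary p-values. This SAP does not secure that. It assigns tests to all secondaries under a general 0.05 level, does not label them nominal, and gives no order, gate or division of alpha. Where it wants description only, it says so and assigns no test (SAP 6.4.4 for subpopulations, 6.5 for safety).

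The gap mattered because the primary missed. The report then moved its weight to secondary p-values at or below 0.05: three VAT endpoints and MPI. Section 11.4.1.4.2 also calls VE/VCO2 at peak exercise statistically significant (p=0.005), although SAP 6.4.2 does not list that endpoint. An efficacy conclusion reached this way carries no 5% limit on the chance of error.

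**Working it through.** **1. Reproduce the reported p-values.** t = LS mean difference / SE, two-sided, df = n − 4 (report Tables 13, 15, 17 and 19).

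| Endpoint | LS mean / SE | t | p recomputed | p reported |
|---|---|---|---|---|
| Maximal VO2, mL/kg/min (primary) | 0.64 / 0.377 | 1.698 | 0.090 | 0.092 |
| Maximal VO2, mL/min | 41.04 / 22.709 | 1.807 | 0.0715 | 0.071 |
| VO2 at VAT, mL/kg/min | 0.78 / 0.308 | 2.532 | 0.0118 | 0.012 |
| VO2 at VAT, mL/min | 41.58 / 18.224 | 2.282 | 0.0231 | 0.023 |
| VE/VCO2 at VAT | −0.82 / 0.321 | −2.555 | 0.0111 | 0.011 |
| Work rate at VAT | 3.20 / 1.460 | 2.192 | 0.0291 | 0.029 |
| MPI | −0.03 / 0.014 | −2.143 | 0.033 | 0.024 |

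The MPI gap is explained by the coarse rounding of −0.03 and 0.014. The mL/min unit for VO2 was added after blind break (report 9.8.2.3).

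**2. Count the family.** SAP 6.4.2 names six exercise secondaries: VO2, VE/VCO2 and work rate at VAT, and respiratory rate, minute ventilation and work rate at peak. Its full list has 15 lines, or 20 endpoints when compound lines are split (my count).

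**3. Holm over the six.** Adjusted p for the j-th smallest = running maximum of (6 − j + 1) × p(j). The three peak endpoints (p = 0.696, 0.915 and 0.891, Table 18) are far from the threshold. Their observed-case p-values are not printed in the text; I assume that they too exceed the VAT values, in which case they do not affect the results below.

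- LOCF, VO2 per kg: VE/VCO2 6 × 0.011 = 0.066; VO2 5 × 0.012 = 0.060, raised to 0.066; work rate 4 × 0.029 = 0.116.
- LOCF, VO2 in mL/min: VO2 becomes 5 × 0.023 = 0.115; the other two are unchanged.
- Observed cases (11.4.1.3 and 11.4.1.4.1), VO2 per kg: VO2 6 × 0.009 = 0.054; VE/VCO2 5 × 0.014 = 0.070; work rate 4 × 0.021 = 0.084.

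**4. Holm over all of SAP 6.4.2, smallest VAT value.**

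- LOCF: 15 × 0.011 = 0.165; 20 × 0.011 = 0.22.
- Observed cases: 15 × 0.009 = 0.135; 20 × 0.009 = 0.18.

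**5. Where the VAT results do survive.**

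- VAT-only family of three, LOCF: 3 × 0.011 = 0.033, and all three are 0.033 with VO2 per kg. With VO2 in mL/min they are 0.033 (VE/VCO2), 0.046 (VO2) and 0.046 (work rate).
- VAT plus MPI, four endpoints: all survive with VO2 per kg (0.044 to 0.048); only VE/VCO2 survives (0.044) with mL/min.
- VO2 at VAT with mean or regression imputation, family of six: mL/min 6 × 0.002 = 0.012 and 6 × 0.003 = 0.018; mL/kg/min 6 × 0.007 = 0.042 and 6 × 0.003 = 0.018.

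**6. Unadjusted error rate.** With m independent true nulls, the chance of at least one p≤0.05 is 1 − 0.95^m: 26% for m=6, 54% for m=15, 64% for m=20. Correlation between endpoints lowers these figures.

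**The case against.** **The SAP can be read as consistent.** Section 6.0 allows for exceptions, and 6.4.5 may be one; secondary analyses beside a single formal test are then nominal. That reading is fair, and it means the report's use of the p-values departs from 6.4.5 at least as much as the SAP rule is at fault. It does not rescue the conclusion: if the secondaries are nominal, they cannot carry an efficacy finding. The report does disclose the lack of adjustment and that the primary was not significant.

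**A reader might infer that no VAT result survives adjustment.** The documents do not support that. The SAP defines no Holm family, and step 5 shows survival in a VAT-only family and under two imputations. There are reasons to discount these: the SAP names no VAT-only family, the report's emphasis on VAT came with a primary that had missed, and both imputations were added after blind break and depart from SAP 6.4.3. They still rule out an absolute statement.

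**Holm is conservative for correlated endpoints.** This stands. The documents give no correlations. If all six endpoints are assumed equally correlated, a min-p adjustment of 0.009 gives 0.053, 0.050, 0.044 and 0.036 at correlations 0, 0.3, 0.5 and 0.7. The observed-case 0.054 is therefore borderline.

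**A gate written now is not prespecified.** This also stands. The SAP was final on 23 June 2016 and the blind was broken on 19 July 2019.

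**Conclusion.** The point holds in this form. The SAP restricts formal testing to the primary but does not carry that restriction into 6.4.2 or 6.0, and the report draws an efficacy conclusion from secondary p-values that 6.4.5 gives no standing. The primary missed at p=0.092 (0.071 in mL/min).

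The Holm figures show only how much the VAT evidence depends on an unstated family: 0.066 to 0.116 (LOCF) or 0.054 to 0.084 (observed cases, VO2 per kg) over six exercise secondaries, and 0.135 or more over the 15 to 20 endpoints of 6.4.2. They rest on my count of the family and on the reported p-values being right. On the latter, the footnotes to Tables 15 and 17 give baseline maximal VO2 as covariate, whereas SAP 6.4.2 specifies the endpoint's own baseline, so those p-values may not come from the planned model.

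It would be wrong to infer that the VAT differences are false positives. The supportable conclusion is that they are exploratory. The primary analysis itself is unaffected.

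**What to change.** 1. **SAP 6.4.5:** state that secondary p-values are nominal and support no significance or efficacy claim if the primary fails. For this trial that is a clarification, not a prespecified rule.
2. **Report 11.4.1, 11.4.1.4.2, 11.4.7 and 13:** label secondary p-values nominal and exploratory, and give estimates with 95% confidence intervals. For example, VO2 at VAT per kg is 0.78 ± 1.967 × 0.308, or 0.17 to 1.39 mL/kg/min. Drop the words statistically significant and the p≤0.05 criterion for secondaries.
3. **Report 11.4.7 and 13:** remove the statements that the study met its primary clinical objective or demonstrated improved exercise capacity.
4. Show any multiplicity-adjusted p-values only as a post hoc sensitivity analysis, with the family named.

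No new data are needed, only wording and intervals computed from the printed estimates and standard errors. The downside is that the VAT and MPI results then read as exploratory.

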6.5 Safety Evaluations

Safety assessments will be summarized for the Safety Population. No formal hypothesis testing will be performed.

6.5.1 Extent of Exposure

The number of days from first to last dose will be summarized descriptively for each treatment group. Percent compliance for the entire study will be calculated as follows:

$$\text{Number tablets missed} = (\text{number returned} - (2 \times \text{number of days off study}))$$

$$\text{Number tablets expected} = 2 \times \text{number of days on study}$$

$$\text{Percent Compliance} = (1 - (\text{number missed} / \text{number expected})) \times 100.$$

A subject will be considered on-study from Visit 1 until study completion or premature discontinuation of study drug. Percent compliance will be summarized descriptively for each treatment group.

CONFIDENTIAL

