Subjects returned to the clinic at Week 26 (study completion/early termination). In addition to clinic visits, study coordinators contacted each subject by telephone the day after the baseline visit to discuss any adverse events (AEs). Subjects were also contacted by telephone at Weeks 1, 2, 3, 4, 8, 13, 17, and 21 to ensure the study drug was well tolerated, to monitor study drug adherence, record AEs and concomitant medications, and offer pregnancy counseling, if needed. Subjects were encouraged to notify the study coordinator between scheduled contact dates with any new onset symptoms or complications.

[figure not shown]
In-clinic study visits included assessments of safety (AEs, concomitant medication use, vital signs, and clinical safety laboratory evaluations), efficacy (exercise testing, echocardiogram, EndoPAT®, BNP, and quality of life measurements), and PK.

The duration of study drug dosing was 26 weeks. When an individual subject completed the study, the subject's primary cardiologist was notified, and the study drug was stopped. All subjects were invited to participate in an open-label, 12-month safety extension study of udenafil. Any subject declining participation in the extension study was to be followed for 90 days at Weeks 30, 34, and 39 for any additional AEs.

Subjects were given the opportunity to participate in the heart rhythm-monitoring subset of FUEL until a total of 25% of all randomized subjects had been included. Heart rhythm monitoring included a 7-day baseline monitor and a 3-day steady state monitor, as described in [Section 9.5.1.2.6](#).

The study design is displayed in [Figure 1](#). The overall schedule of assessments is provided in [Table 2](#). [Table 3](#) presents procedures performed before and after the first dose of study drug in the clinic at Visit 1.

Figure 1: Study Design

AE=adverse event; BNP=brain natriuretic peptide; BP=blood pressure; ECG=electrocardiogram; echo=echocardiogram; EST=exercise stress test; FUEL=Fontan Udenafil Exercise Longitudinal Assessment Trial; LV=left ventricular; min=minute; OLE=open-label extension; PK=pharmacokinetic; RV=right ventricular; yrs=years

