9.4.2 Identity of Investigational Product(s)

9.4.2.1 Study Drug

A description of study drug is provided below.

Dosage form description	Pale-orange, oval-shaped, film-coated tablets of 87.5 mg udenafil or matching placebo (0 mg drug). Tablet inactive ingredients: lactose monohydrate, corn starch, low substituted hydroxypropyl cellulose, hydroxypropyl cellulose, talc, magnesium stearate, colloidal silicon dioxide, hydroxypropyl methylcellulose, titanium dioxide, FD&C Yellow No. 6 Aluminum Lake, and iron oxide red.
Package description	One plastic bottle of 60 tablets per bottle.
Manufacturer	[name] Ltd., [name].
Dosage per time unit	One tablet orally twice a day.
Storage	Udenafil tablets were to be stored at 20°C to 25°C (68°F to 77°F); excursions were permitted to 15°C to 30°C (59°F to 86°F). The study drug must have been protected from unauthorized access (eg, in a locked storage facility). Any unused, partially used, or empty bottles of study drug were destroyed at the site at the time of the site's close-out visit. Destruction of the study drug was properly documented on forms provided by the Sponsor or designee.
Batch number	UDBT15-10 (udenafil); P1MT15-09 (placebo to match udenafil)

Subjects receiving each batch of study drug are identified in [Appendix 16.1.6](#).

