9.4.2.3 Accountability

The Site Principal Investigator had overall responsibility for the use of the study drug. The Site Principal Investigator or designee confirmed receipt of the study drug by signature and date, and returned a duplicate copy of receipt to the Sponsor or designee.

Under no circumstances was the Investigator to allow the investigational drugs to be used other than as directed by the protocol. Qualified study personnel used the specified randomization system to assign subjects to treatment and maintained accurate study drug-dispensing records regarding the date and amount dispensed to each subject. Reasons for digression from the expected dispensing regimen were to be recorded. The study drug inventory record was available for inspection by representatives of the Sponsor and was subject to regional regulatory authority inspection at any time. At the conclusion of the study, the Site Principal Investigator provided a copy of this record to the Sponsor.

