5.0 Study Procedures

Study procedures will be performed as outlined in **Error! Reference source not found.**. In-clinic procedures associated with the first dose of study drug at Visit 1 are outlined in Table 1.

CONFIDENTIAL

Table 1 Schedule of Measurements/Events

Visit Number	1	TC1	TC2	2	TC3-5	3	TC6-7	4	TC8-10
Time point	Screening/ Baseline Day 0	Day 1	Week 1	Week2	Weeks 3, 4, 8	Week 13	Week 17, 21	Week 26	Week 30, 34, 39
Visit Window(s)			± 3 days	± 3 days	± 3 days	±10 days	± 3 days	±10 days	± 10 days
Type of Visit(s)	In-Person	Call	Call	In- Person	Call	In- Person	Call	In- Person	Call
Informed Consent/Assent	X								
Subject ID# assigned	X								
Inclusion/Exclusion Criteria	X								
Physical Measurements	X								
Medical history	X								
Demographics/expanded demo	X								
Prior/Concomitant Meds	X		X	X	X	X	X	X	
EndoPAT®	X								X
Serum or urine pregnancy test^a	X			X		X		X	
Clinical Laboratory tests (creatinine, ALT, AST)	X								X
Biomarker (BNP) sample	X								X
Genetic repository sample (optional)	X ^a								X ^b
Echocardiogram	X								X
Exercise test	X ^c								X ^c
Randomization	X								
Dispense Study Drug	X			X		X			
Resting BP and HR	X			X		X		X	
Administer first dose of study drug (see Additional Procedures and Measurements in Table 2)	X								
Peds QL generic and cardiac modules; PCQLI; HAES	X								X
Drug Accountability	X		X	X	X	X	X	X	
Pregnancy counseling (if applicable)	X		X	X	X	X	X	X	
Adverse events assessment	X	X	X	X	X	X	X	X	X ^a
Morisky Scale (MMAS)			X		X		X		
Schedule/Confirm next visit	X	X	X	X	X	X	X	X	

^aas applicable^bas applicable if missed at baseline visit^cBaseline visit: If failed 1st exercise test, do NOT randomize; At baseline and Week 26 visits, at Site Investigator's discretion, exercise test may be repeated w/in 14 days -- If a second exercise test needed, you MUST perform urine (or blood) pregnancy test for eligibility (if applicable).

CONFIDENTIAL

Table 1 Schedule of Assessments at Visit 1

Procedure	Time From Administration of First Dose of Study Drug			
	< 1 Hour Prior to Dose	0 Hour	2 Hours (± 30 Minutes)	4 Hours (± 30 Minutes)
Resting vital signs ^a	X			X ^b
Administer first dose of study drug		X		
Vital signs immediately before and following a 6-minute self-limited walk			X	
Pharmacokinetic blood sample immediately after 6-minute walk			X	
Record adverse events		X	X	X
Dispense study drug for home administration				X
Discharge from clinic				X

a Includes blood pressure and heart rate.

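### The SAP 6.5.1 percent-compliance formula leaves out tablets dispensed and does not define days off study, so it is right only for one exact supply per subject

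*SAP*

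**What the plan says.** SAP 6.5.1, repeated in Protocol Section 9.7.1.5.1, scores compliance over the whole study as 100 × (1 − missed/expected). Missed is the tablets returned minus twice the "number of days off study". Expected is twice the "number of days on study". The second period is defined: "A subject will be considered on-study from Visit 1 until study completion or premature discontinuation of study drug". The first has no definition, and in particular no end date. The section has no term for tablets issued, no rule for bottles that never come back, and no cap.

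On supply, Protocol Section 9.4.2.1 gives "One plastic bottle of 60 tablets per bottle" and "One tablet orally twice a day", so a bottle lasts 30 days. Section 9.1 adds: "The duration of study drug dosing was 26 weeks". The "Dispense Study Drug" row of the schedule in SAP 5.0 is marked at Visits 1, 2 and 3. Table 2 in Protocol Section 9.5.1 marks dispensing at Visit 1 only, Visits 2 and 3 having become telephone calls (Section 9.8.1). Section 9.4.8 describes resupply as needed. No section states how many bottles a subject received. Section 9.4.2.3 does say that qualified staff "maintained accurate study drug-dispensing records regarding the date and amount dispensed to each subject", so the quantities exist.

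**The concern.** Protocol Section 9.4.8 presents adherence as a comparison of expected with actual consumption. Consumption is what was issued minus what came back, and the formula uses only what came back. Leftover tablets then count as missed doses unless days off study happens to offset them. Where supply was short of the full course, the offset can exceed the leftovers and the number missed becomes negative. The score then depends on bottle count, visit timing and the reading given to an undefined term, as well as on adherence.

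At stake are the report's tablet-count compliance figures, means of 89.92% (udenafil) and 89.97% (placebo), given in Sections 11.3 and 12.1. A reader cannot tell what level of adherence they represent.

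**Working it through.** **Reported figures.** Table 23 (Protocol Section 12.1) gives means of 89.92% (n = 174) and 89.97% (n = 185), medians of 92.89% and 93.20%, and ranges of 48.5 to 100.0 and 39.6 to 100.0. The weighted mean is (174 × 89.92 + 185 × 89.97)/359 = 89.946, which agrees with the stated 89.94 within rounding. The arm means cannot be rebuilt, because neither document gives tablets dispensed or returned. Subjects without a value: 200 − 174 = 26 udenafil and 200 − 185 = 15 placebo, 41 in all.

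**What the formula measures.** Let D be tablets issued, T tablets taken, and suppose every leftover is returned, so returned = D − T. Then

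score = 1 − (D − T − 2·off)/(2·on) = T/(2·on) − [D − 2·(on + off)]/(2·on).

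The first term is true compliance. The second is an error that vanishes only if D = 2·(on + off).

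**Fully adherent completer, off = 0.** The bottle count is an assumption. Seven is the fewest whole bottles that cover 182 days (364 tablets; six hold 360).

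| Days on | Bottles (tablets) | Returned | Score |
|---|---|---|---|
| 180 | 6 (360) | 0 | 100% |
| 182 | 7 (420) | 56 | 1 − 56/364 = 84.6% |
| 182 | 8 (480) | 116 | 1 − 116/364 = 68.1% |
| 172 | 7 (420) | 76 | 1 − 76/344 = 77.9% |
| 192 | 7 (420) | 36 | 1 − 36/384 = 90.6% |

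The last two rows are the edges of the ±10-day Week 26 window. The same perfect adherence differs by almost 13 points on visit timing alone. If off were instead read as the 28 surplus days of supply, the 182-day, seven-bottle subject would score 100%.

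**Fully adherent subject who stops at day 30.** Expected = 60. If off runs to Week 26, off = 182 − 30 = 152 and 2·off = 304.

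| Issued | Returned | Score, off = 152 | Score, off = 0 |
|---|---|---|---|
| 60 | 0 | 1 + 304/60 = 607% | 100% |
| 120 | 60 | 1 + 244/60 = 507% | 0% |
| 364 | 304 | 100% | −407% |
| 420 | 360 | 1 − 56/60 = 6.7% | −500% |

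Such subjects existed: Table 5 shows 12 + 9 = 21 who stopped study drug early, and the shortest exposure in Table 23 is 5 days.

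**With tablets dispensed included.** (D − returned)/(2·on) gives (420 − 56)/364 = 100% for the seven-bottle completer and (60 − 0)/60 = 100% for the one-bottle stopper.

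**Unreturned bottles, a separate matter.** Take a 182-day completer issued seven bottles who took 304 of 364 tablets (83.5%). If all 116 leftovers come back, the SAP formula gives 68.1% and the dispensed-minus-returned formula 83.5%. If one full bottle is lost (56 returned), they give 84.6% and 100%. Both rise by 16.5 points. A subject who takes nothing and returns nothing scores 100% under the SAP formula and 420/364 = 115.4% under the other.

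**The case against.** The strongest reply is that every percentage above is a scenario. Bottle size alone does not yield 84.6%: that also needs seven bottles, 182 days and zero days off. The 507% needs staged supply and a count of days off that runs to Week 26; with the full supply issued at the start the error reverses. This stands. The direction of the error in the actual data is unknown.

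Table 23 also argues against 85% as a usual ceiling. With seven bottles and full return, a perfect subject at the median exposure of 183 days scores 1 − 54/366 = 85.2%, yet the reported medians are about 93%. Supply, the reading of days off, or the return of leftovers must have differed from that scenario for many subjects.

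A reader might infer from the maximum of exactly 100.0% that values were capped or the formula was not followed. That does not follow. With off = 0 and returned tablets never negative, the formula cannot exceed 100%. Only early stoppers could, and they may be among the 41 without a value. The documents do not say.

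A reader might also blame lost bottles counting as taken on the missing dispensed term. The working shows that dispensed-minus-returned shares this weakness, so it needs its own rule.

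None of this supplies a definition of days off study or a reason to expect D = 2·(on + off).

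**Conclusion.** The point holds as a minor one. Followed as written, SAP 6.5.1 returns true compliance only when each subject's supply equals 2 × (days on + days off) tablets. Nothing in the documents secures that, and one of the two periods is undefined. Under assumed bottle counts, perfect adherence scores from 68.1% to 100% for a completer with zero days off, and from 6.7% to 607% for a day-30 stopper if days off run to Week 26. These show how sensitive the rule is; they do not estimate the error in Table 23.

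The consequence is confined to the 89.92% and 89.97% and their ranges. One might suppose that the figures support the efficacy conclusions, the Per Protocol population or the study-medication deviation in Table 6. The efficacy conclusions do not cite compliance. The Per Protocol definition (SAP 6.1) has no compliance cut-off, and SAP 8.0 records that the dosing-compliance population was dropped. Nothing ties the Table 6 category to this formula. The primary and Per Protocol efficacy analyses are unaffected.

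**What to change.** - Replace the formula in SAP 6.5.1 with percent compliance = (tablets dispensed − tablets returned) / (2 × days on study drug) × 100, using the recorded dispensing amounts. Days off study then drops out; if the term is kept anywhere, define its start and end.
- State separately how unreturned bottles are handled. Setting such subjects to missing is one option, but it may selectively remove poor adherers, so report their number by arm.
- State how values above 100% are handled.
- Rerun Table 23 and explain the 41 of 400 subjects with no value (26 udenafil, 15 placebo), including how many are early stoppers and how many had unreturned bottles.

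The cost is one formula, two sentences of rules and one rerun table. No new data are needed if the dispensing and return records are complete.
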